Social Factors: We will evaluate the following factors: marital status, years of education, type of work, tobacco history (pack years, current smoker, current use of chewing tobacco, previous smoker, no tobacco history).

Questionnaires: We will ask the subject to answer a series of health related questionnaires such as quality of life (Promise Global), demographics, anxiety (Beck Anxiety Scale), Pain-Mobility, fear of falling (FES-I), frailty (Fried Frailty), MOCA for cognitive status, and depression (CES-D), Trail-making task A and B, LifeSpace, ePro Lawton and Katz Scale for daily activities. We will also ask them to fill out an acceptability questionnaire at the follow up visit.

Peripheral Neuropathy: We will use Vibration Perception Threshold (VPT) testing, evaluated at the distal great toe, heel and 5th metatarsal.

Gait assessment: Gait performance will be assessed using a validated body worn sensors (LegSys_z, Biosensics LLC, USA). The device uses five sensor modules respectively attached to right and left anterior shins, right and left anterior thighs, and posteriorly to the lower back. Based on the subject's height and using a two-link inverse pendulum model the following spatio-temporal gait parameters will be estimated: velocity, stride length, stride time, double support, single support, stride-to-stride variability, and gait initiation. In addition, the center of mass (COM) range of motion during walking will be calculated by using the data from the sensor attached to lower-back. Gait will be assessed over a distance of 20 meters under 2 conditions: (1) walking at habitual speed (2) walking at maximum speed (fast walking).

Balance assessment: Balance will be quantified using validated body worn sensors (BalanSens_z, Biosensics LLC, USA). The system measures ankle and hip motion in three dimensions (3D), 2D COM sway as well as RCI in ML and AP directions. Balance will be assessed according to Romberg protocol during eyes-open and eyes-closed condition during double, semi-tandem, and full tandem stances.

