Please indicate why you chose the sample size proposed:

For Phase I: Considering the timeline and budget limitation, the sample size is limited to 15 subjects. Size was estimated based on preliminary study, described in detail in the research strategy document, in which we have demonstrated that 4-weeks exergame program significantly reduce center of mass (COM) sway in aMCI patients with an effect size of 0.83 compared to baseline. Assuming a pairwise comparison using t-test, 80% power, alpha of 5%, 14 subjects should be sufficient to observed significant difference in balance compared to baseline. For phase II: The sample size was calculated based on our preliminary study described above for training-related improvement in balance (quantified by CoM sway area in medial-lateral direction during eyes-open stance), fear of falling (quantified by FES-I), and cognitive function (quantified by TMT) post exercise in people with confirmed amnestic MCI. Our preliminary results suggested that prior Exergame, COM sway in was 1.60 ± 0.76 cm² and was improved to 1.05 ± 0.44 cm² post Exergame intervention (Cohen's effect size $d=0.83$). Assuming a pairwise comparison using t-test, 80% power, alpha of 5%, 14 subjects should be sufficient to observed significant difference in balance compared to baseline. Our preliminary study has also suggested that FES-I was significantly improved post exercise compared to baseline with an effect size of 1.14, suggesting a sample size of 9 to

observe benefit for fear of falling. Finally, effect size for improvement in TMT A post exercise was 0.42. Thus using similar assumptions described above, the needed sample size for observing benefit for cognitive function is 46. Assuming approximately 10% drop out, we plan to recruit 50 subjects per group, for a total of 100 subjects.

G2. Data Analysis

Provide a description of your plan for data analysis. State the types of comparisons you plan (e.g. comparison of means, comparison of proportions, regressions, analysis of variance). Which is the PRIMARY comparison/analysis? How will the analyses proposed relate to the primary purposes of your study?

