(For both phases) We will used paired t-test (for normally distributed outcomes) and Mann-Whitney U-tests (for non-parametric outcomes) to determine the effect of intervention at 6 weeks. To examine whether the benefit of exercise is dependent on sex (sex as biological factor), we will compare the gain in balance improvement between male and female using Mann-Whitney U-test. We recognize that the study is under power for assessing the effect of confounders (e.g. age, baseline cognitive performance, baseline motor performance, BMI, etc). However, we determine whether the magnitude of gain is correlated with any of these confounders using Spearman correlation of coefficient change. During Phase II, these confounders will be controlled as covariant and between and within group comparisons will be adjusted.

Section H: Potential Risks/Discomforts

H1. Potential Risks/Discomforts

Describe and assess any potential risks/discomforts; (physical, psychological, social, legal, or other) and assess the likelihood and seriousness of such risks:

The measuring systems including LEGSys (for assessing gait and balance), BalanSens (for assessing balance), and PAMSys (for monitoring spontaneous daily physical activities) , as well as the iTMT platform are battery-powered, self-contained units and used in many clinical studies including patients with MCI and AD, and no adverse report were reported. Except activity monitoring, the rest of assessments including gait and balance will be performed in a control environment. As these devices are attached using elastic straps, research staff will ensure these are comfortably tight on the participant to avoid any pain or poor blood flow.

For home assessment, PAMSys (will be used for daily physical activity monitoring and daily motor performance such as postural transition) is worn in a shirt or vest pocket and does not rest directly against subjects' skin. Thus, wearing the PAMSys, poses no risks to subjects. All wearable sensors, which will be used in this study meet the requirements for IDE exemption under 21 CFR 812.2(c), Category 3.

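### G2 names baseline cognitive and motor performance as example Phase II covariates but not baseline FES-I; stating that each outcome's own baseline is adjusted for would sharpen the between-arm fear-of-falling comparison at almost no cost

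*Combined protocol and SAP*

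**What the plan says.** **Covariates (G2, Data Analysis).** The examples given are "confounders (e.g. age, baseline cognitive performance, baseline motor performance, BMI, etc". For Phase II, G2 then says: "During Phase II, these confounders will be controlled as covariant and between and within group comparisons will be adjusted". This is the only adjustment rule in the plan. It does not name the model, does not say whether the response is the follow-up value or the change, and does not say whether the covariates are the same for every outcome.

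**FES-I as a sizing outcome (G1, Sample Size).** Phase II is sized on sway, FES-I and TMT. For FES-I, G1 reports that "FES-I was significantly improved post exercise compared to baseline with an effect size of 1.14" and derives a sample size of 9. Balance gives 14 and TMT A gives 46. All three are within-group, pre-post calculations.

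**FES-I at baseline (F2, Procedure).** The questionnaire list includes "fear of falling (FES-I"), and the Phase II paragraph of F2 repeats the Phase I questionnaires at each in-person visit. The baseline score will therefore be on file.

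**The concern.** Of the three sizing outcomes, two have a baseline counterpart among the named covariates: cognition for TMT, and motor performance for sway. Fear of falling is a self-reported questionnaire score and is neither of these. An analyst who adjusted only for what G2 names would compare the arms on FES-I without using the earlier measurement of the same scale, which is usually the strongest predictor available.

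What is at stake is precision in the remote-versus-supervised contrast on FES-I. There is a second, smaller matter. Because the list is open, baseline FES-I could be put in or left out after the data have been seen.

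**Working it through.** **1. The plan's own figures.** The approximate paired sample size is n = (1.960 + 0.842)²/d² + 1.96²/2 = 7.849/d² + 1.92 (two-sided 5%, 80% power; G1 does not state sidedness).

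- d = 1.14: 6.04 + 1.92 = 7.96. The exact noncentral t calculation gives 9, as stated (power 84.9%).
- d = 0.83: 11.39 + 1.92 = 13.31, so 14, as stated (power 81.9%).
- d = 0.42: 44.49 + 1.92 = 46.41, so 47. The stated 46 gives 79.6%, which is close enough.

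The figures reproduce as paired calculations. None of them is a between-arm effect.

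**2. Inputs for the between-arm comparison.** From G1: 50 per arm and about 10% dropout, so 50 × 0.90 = 45 evaluable per arm. Assumed, because the documents do not give them: the pre-post correlation ρ of FES-I, the between-arm difference d (in SDs of a single FES-I measurement), equal SDs before and after, and no FES-I variance explained by the named covariates.

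**3. Variance, with a single-measurement SD of 1.**

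- Follow-up score alone: 1
- Change score: 2(1 − ρ)
- Follow-up adjusted for its own baseline: 1 − ρ²

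The adjusted variance is therefore 1 − ρ² of the follow-up variance, and (1 + ρ)/2 of the change-score variance. At ρ = 0.5 both ratios are 0.75, so the result does not depend on which response G2 intends. The confidence interval shrinks by 1 − √0.75 = 13.4%. Equivalently, 45 per arm does the work of 45/0.75 = 60.

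**4. Power at ρ = 0.5, 45 per arm, two-sided 5%, noncentral t.**

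| Assumed between-arm d | Without baseline FES-I | With baseline FES-I | Gain (points) |
|---|---|---|---|
| 0.20 | 15.5% | 19.2% | 3.6 |
| 0.30 | 29.1% | 36.9% | 7.8 |
| 0.35 | 37.5% | 47.5% | 9.9 |
| 0.42 | 50.4% | 62.4% | 11.9 |
| 0.50 | 65.0% | 77.3% | 12.3 |
| 0.60 | 80.4% | 90.2% | 9.8 |
| 0.70 | 90.7% | 96.7% | 5.9 |

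(Gains are from unrounded values.)

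**5. Sensitivity to ρ, starting from 80% unadjusted power (normal approximation).**

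| ρ | Gain over change score | Gain over follow-up score alone |
|---|---|---|
| 0.3 | 13.5 | 3.6 |
| 0.5 | 9.9 | 9.9 |
| 0.7 | 6.0 | 17.5 |
| 0.8 | 4.0 | 19.7 |

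Against change scores, over starting powers from 30% to 95%, the gain never exceeds about 7 points at ρ = 0.7 or 4.5 points at ρ = 0.8.

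**6. If the named covariates already help.** Suppose they explain 10% of FES-I variance, and the total with baseline FES-I stays at 25%. The variance ratio becomes 0.75/0.90 = 0.83. The gain falls to 7.8 points at d = 0.42, 7.6 at 0.50 and 5.7 at 0.60 (normal approximation).

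**7. Chance imbalance.** The standard error of the baseline difference between arms is √(2/45) = 0.21 SD. A one-standard-error imbalance shifts a change-score contrast by (1 − ρ) × 0.21, about 0.1 SD at ρ = 0.5. Adjustment for baseline removes this shift in the sample at hand.

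**The case against.** The strongest objection is that the list is only illustrative, so baseline FES-I is not named but is not excluded either. That stands. A reader might infer that the plan has decided to leave baseline FES-I out, and the text does not support this. An open list nevertheless commits the analyst to nothing, and nowhere does the plan say that an outcome's own baseline is used.

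A reader might also infer that Phase II will compare change scores. G2 mentions gain only in the comparison of men and women and in the Spearman correlations. The Phase II sentence leaves the response open.

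Nor do the documents support saying that chance baseline differences bias the result. The arms are randomised, so the unadjusted contrast is unbiased on average and its standard error already reflects chance imbalance. What remains is lost precision and a shift conditional on the imbalance that happens to occur.

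Finally, it can be said that FES-I does not drive the sample size (9 against 46 for TMT A), and that at d = 1.14 adjustment gains nothing. The first is true and limits the weight of the point. The second has little force: 1.14 is a pre-post effect within one group, whereas both Phase II arms do the same exercise programme and differ in delivery. For the same reason a between-arm difference below 0.35 SD is quite possible, and the power gain would then be under 10 points at ρ = 0.5.

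**Conclusion.** The point holds as an inexpensive improvement, not as an error in the plan. G2 should say that each outcome's own baseline is adjusted for; FES-I is the sizing outcome for which the named examples offer no baseline counterpart.

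The firmest statement of size needs no between-arm effect: at ρ = 0.5 the variance falls to 75% and the interval narrows by about 13%, given equal SDs and named covariates that explain no FES-I variance. A reader might want to quote a flat loss of 10 to 12 power points. That figure also requires a between-arm difference of about 0.35 to 0.60 SD with 45 per arm. It is smaller for differences outside that range, if the named covariates already predict FES-I, or, against change scores, if ρ exceeds about 0.7. Confidence in the recommendation is good; confidence in any single power figure is low, because neither ρ nor a between-arm effect is in the documents.

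**What to change.** Add a sentence to G2 along these lines: each Phase II between-arm comparison models the follow-up score, with that outcome's own baseline value as a covariate in addition to the listed covariates; for fear of falling this is baseline FES-I.

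This also settles the response form for the between-arm comparisons and removes the choice about own-baseline adjustment from the analysis stage. FES-I is already scheduled at baseline, so no new data are needed. The cost is one sentence and one degree of freedom per model, which is negligible with about 90 evaluable participants.

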Phone calls: We will contact subjects at three and six months after their follow up visit to ask if they have had any accidental falls and other questions regarding their health. Research Coordinators may also call subject for study related questions.

Photos and media: We will be asking permission of the subject to take photos, film videos and/or record audio during the visits in order to monitor their progress throughout the study. Additionally, these photographs might be used for scientific publications/ oral presentations. If the subject's face is in the photo, as per journal policy, we will cover their face.

Phase II: The study will consist of a 12 week exercise program with one baseline, 24 exercise sessions, 6 weeks follow up, 12 weeks follow up, 6 months follow up, and 12 month follow up.

The same questionnaires and physical assessments will be completed at each in person visit as Phase I. In Phase II, 100 subjects will be randomized into either intervention or control group. All recruited subjects will undergo to 12 weeks exercise program using the Exergaming platform described in the proposal, twice per week for approximately 30 minutes. The intervention group will be given the Exergaming system and will perform the 24 exercise sessions remotely. The control group will perform the exercise sessions in person under supervision with the Exergaming system. The first four sessions (week #2), subjects are asked to perform six blocks (each approximately takes 5 min to be completed) of consecutive ankle reaching tasks in upward-downward (i.e. ankle flexion-extension) direction and side-ward reaching task (foot inversion-eversion). They could have reset between each block of exercise before starting the next block. Starting the 5th session (week #4), reaching tasks on diagonal directions are added, which is required the combined foot inversion-eversion and ankle flexion-extension. To keep the duration of exercise constant, a block from simple reaching task is replaced by a new complex reaching task. From the 11th session (week #6), motor-cognitive tasks as described in the following will be added. The tasks make the program more challenging and fun, in addition to potentially having a secondary benefit for older patients who may struggle to execute motor-cognitive tasks.

Section G: Sample Size/Data Analysis

G1. Sample Size

How many subjects (or specimens, or charts) will be used in this study?

Local: 115 Worldwide: 115

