Describe potential benefit(s) to be gained by the individual subject as a result of participating in the planned work.

Phase I: There is no direct benefit to participating subjects as this is a pilot study and their participation will help improve further research in this population.

Phase II: We cannot promise any benefit to you or to others from joining this research. However, possible benefits include enhancing the subject's balance and walking ability. In addition, what the researchers find out from this study may help other people with poor balance as well as those suffering from MCI and mild dementia.

Describe potential benefit(s) to society of the planned work.

The main benefit to subjects is the positive feeling that they will have by participating in a study that will potentially help other people by developing new technology that could assist them to maintain mobility, preserve their cognitive, and promote aging in place and independency. They might eventually directly benefit from this technology if they purchase it in the future. In addition, all participants will provide validated exercise interventions, which have been showed to be effective to improve balance and mobility in people with dementia and MCI. The subjects will be compensated for their time (\$50 per visit either in clinic for baseline assessment or at home when study investigators will visit them at home). In the Phase II, participant will be compensated \$10 per exercise session as well. During Phase II for the control group, who needed face-to-face exercise, their parking fee and/or transport (up to \$50) would be compensated. Except baseline screening and post exercise evaluation, no any clinic visit is needed for the intervention group. At the end of the study, a research investigator will collect the teleexergame platform from the intervention group.

Do anticipated benefits outweigh potential risks? Discuss the risk-to-benefit ratio.

While the risk is anticipated to be minimal as described above, the gained knowledge is significant and may assist us to translate a practical, low cost, and personalized game-based exercise platform in a secure and remote setting to enhance balance, mobility, and quality of life of patients with MCI and mild dementia.

Section J: Consent Procedures

J1. Waiver of Consent

Will any portion of this research require a waiver of consent and authorization?

Yes

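### G2 analyses Phase II at week 6, mid-programme, when Section I requires no clinic visit of the remote arm; where either arm is then tested is not stated

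*Combined protocol and SAP*

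**What the plan says.** All references are to the combined protocol and SAP.

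- **Section G2 (Data Analysis)**, in a paragraph that covers both phases, gives paired t-tests and Mann-Whitney tests "to determine the effect of intervention at 6 weeks". It names no other analysis time. It also promises adjusted comparisons between and within groups in Phase II.
- **Section F2 (Procedure), Phase II**: "The study will consist of a 12 week exercise program with one baseline, 24 exercise sessions", then "6 weeks follow up, 12 weeks follow up, 6 months follow up, and 12 month follow up". This schedule is not split by arm. On content it says: "The same questionnaires and physical assessments will be completed at each in person visit as Phase I". Controls exercise in person under supervision; the intervention arm does all 24 sessions remotely.
- **Section H1 (Potential Risks/Discomforts)**, after setting activity monitoring aside: "the rest of assessments including gait and balance will be performed in a control environment". The next paragraph, on assessment at home, names only the PAMSys activity monitor.
- **Section I (Potential Benefits)**, just after the reimbursement of controls' parking and transport: "Except baseline screening and post exercise evaluation, no any clinic visit is needed for the intervention group". The same section sets a payment "per visit either in clinic for baseline assessment or at home when study investigators will visit them at home", which is not limited to one arm.
- **Section L (Cost/Payment)** pays for each completed baseline and follow-up visit and names no place.

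**The concern.** Two problems meet at week 6. First, the only analysis time in G2 suits Phase I, whose programme ends at 6 weeks, but in Phase II it falls halfway through the intervention. Second, week 6 is a time at which Section I asks no clinic attendance of the remote arm, while the controls are already coming in for their sessions.

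Phase II compares remote with supervised delivery. Sensor-measured sway and a 20 m walk can plausibly depend on the space and surface where they are done. If the remote arm were tested at home and the controls in the clinic, setting would travel with arm, and the covariate adjustment in G2 could not separate the two. If some remote participants were not tested at week 6, the stated analysis would lose data in the arm under test. The argument concerns the gait and balance tests. No setting effect is claimed for the fear-of-falling questionnaire or for the paper Trail Making Test, which drives the Phase II sample size.

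**Working it through.** The plan states no figure on this point, so the check is mainly a comparison of passages, followed by an illustration on assumed values.

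**1. What week 6 measures in Phase II.** At two sessions a week (F2), 6 × 2 = 12 of 24 sessions are done by the end of week 6, which is half. F2 adds the motor-cognitive tasks from session 11. They therefore belong to 24 − 10 = 14 sessions, of which at most 2 (sessions 11 and 12) fall within the first six weeks. A week-6 analysis largely precedes that component.

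**2. Which follow-ups Section I leaves without a required clinic visit.** The post-exercise evaluation is not dated. The programme lasts 12 weeks, so it cannot be week 6. It may mean week 12 only, or it may also cover 6 and 12 months. Between one and three of the four follow-ups are affected, and week 6 is affected on either reading.

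**3. Possible arrangements at week 6, set against the text.**

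| Week-6 gait and balance tests | Section I | H1 | F2 schedule | Consequence |
|---|---|---|---|---|
| Both arms in clinic | conflicts for remote arm | fits | fits | arms balanced |
| Remote at home, controls in clinic | fits | sits badly | fits | setting differs by arm |
| Both arms at home | fits | sits badly | fits | arms balanced, but change from a clinic baseline includes a change of setting |
| Remote arm not tested | fits | no bearing | departs from it | no week-6 comparison |

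No section chooses between these. The payment total in Section L does not help: its 270 dollars equals 3 × 50 + 12 × 10, which is the Phase I pattern of three visits and twelve sessions.

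**4. Illustration of a setting shift.** G1 plans 50 per group with about 10% dropout, so 50 × 0.9 = 45 evaluable per arm. The standard error of a between-arm difference, in SD units, is √(2/45) = 0.211. With no true difference and an assumed shift b between arms, the rejection rate of a two-sided 5% test is 1 − Φ(1.96 − b/0.211) + Φ(−1.96 − b/0.211), by normal approximation.

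| Assumed shift b (SD) | False-positive rate |
|---|---|
| 0.1 | 7.6% |
| 0.2 | 15.8% |
| 0.3 | 29.6% |
| 0.5 | 66% |

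**5. Illustration of missing remote-arm values.** The detectable difference at 80% power is (1.96 + 0.84) × √(1/45 + 1/n), where n is the number of remote participants with week-6 data.

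| Remote-arm values missing (assumed) | n | Detectable difference (SD) |
|---|---|---|
| 0% | 45 | 0.59 |
| 25% | 33.75 | 0.64 |
| 50% | 22.5 | 0.72 |
| 75% | 11.25 | 0.93 |

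The shifts and the missing fractions are assumptions; the documents give neither.

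**The case against.** The best defence is that Section F2 is the visit schedule and Section I is not. F2 puts a 6-week follow-up in Phase II for everyone, Section L pays for each completed follow-up, and Section I itself foresees paid home visits by study staff. The Section I sentence follows one about travel costs and reads naturally as a remark on travel burden. The absence of a required clinic visit does not mean the absence of an assessment. A staff-run home visit in both arms could also be called a controlled environment, since H1 does not name the clinic.

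Most of this stands. A reader might infer that the remote arm has no week-6 data, that setting is fully confounded with arm, that the passages cannot all be true together, or that three of the four follow-ups are certainly affected. The documents support none of these. A follow-up is scheduled for both arms, home visits are not limited to one arm, the controls' in-person attendance is stated only for exercise sessions, and the post-exercise evaluation is undated.

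It can also be said that moving the analysis to week 12 answers a different question from fixing the setting. That is fair, but both problems arise from the same rule in G2, and one change to that rule goes a long way on both. What the defence does not supply is a statement of where either arm is tested at week 6, or a reason to read the Phase II effect halfway through the programme.

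**Conclusion.** The point holds in a limited form. The firm part is that G2's only time point is mid-programme in Phase II, and that Section I requires no clinic visit of the remote arm then. The place of testing at week 6 is not given for either arm. A clinic test of the remote arm conflicts with Section I, and a home test is hard to square with H1, so incomplete remote-arm data or a setting difference between arms cannot be excluded. That either will happen is not established.

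The size is unknown. The 16% to 30% false-positive range requires an assumed shift of 0.2 to 0.3 SD, every remote participant tested at home, every control in the clinic, and 45 evaluable per arm. It shows that a modest shift would matter in a trial of this size; it does not estimate what will occur. The plan should be changed because the change is specific and cheap and because it lets Phase II compare the two complete programmes.

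**What to change.** - In G2, make the 12-week post-exercise evaluation the Phase II analysis time point and keep week 6 as a secondary interim measure. Phase I can stay at 6 weeks, which is the end of its programme.
- Reconcile Section I with F2 and H1: state the date or dates of the post-exercise evaluation, and state where each Phase II follow-up takes place in each arm.
- Require that any Phase II gait and balance assessment used to compare the arms is done in the same setting and by the same procedure in both. Where change from baseline is analysed, say whether the setting matches baseline.

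The cost is protocol and consent wording. There may also be a few more reimbursed trips for the remote arm, or a few more staff home visits, depending on the setting chosen. The sample size need not change for this.
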